## PROTOCOL VERSION HISTORY

Version	Rationale for amendment	Main changes to the protocol
1.0 / 29 March 2018	Initial version	N/A
2.0 / 26 June 2018	

-To revise the contact information on the cover page.

-To update the restriction of emollient use prior to each study visit.

-To add phototherapy as exclusion criteria.

-To revise the exclusion criterion related to prior use of SYK or JAK inhibitor

-To update the Schedule of Events to clarify that no drug administration will be given at Week 12 visit as part of the present study.

-To clarify the moment when some assessments are to be taken during the visits.

	

-Cover page, sponsor contacts were revised and the name of local medical monitor, email address, telephone number, and fax number were added for the US/Canada medical monitor.

-Synopsis (inclusion criterion #9), Section 5.1 (inclusion criterion #9), and Section 6.4.1., the restriction of emollient use prior to each study visit was modified and specific timing was removed. No emollient is allowed the day of each visit, before the visit.

-List of Abbreviation, Synopsis, Section 5.2, and Section 6.4.2., the following exclusion criteria were added and corresponding sections were revised accordingly:

"Subject has received any UV-B phototherapy (including tanning beds) or excimer laser within 4 weeks prior to Day 1.

Subject has had psoralen-UV-A (PUVA) treatment within 4 weeks prior to Day 1."

-Synopsis and Section 5.2, to clarify the exclusion criterion related to prior use of SYK or JAK inhibitor to restrict only the systemic products.

-Section 1.3, Schedule of Events, check was removed at Week 12 at the line "Study product administration at study center" and the corresponding footnotes were revised accordingly.

-Schedule of event, footnotes #7, #8 and 15, clarification was added with regards to the moment these assessments are to be performed, prior to the study drug administration.

	

-To detail how subjects who start to use prohibited medications for AD during the study will be handled.

-To remove the exclusion of certain body parts for the BSA calculation.

-To correct typographical errors.

	

-Synopsis, Schedule of event (footnote), Sections 5.3.1, 6.4.2, 8.3.1 and 8.3.2, to specify how subjects who start medication for AD during the study are handled and if study product discontinuation is required or not. Specifications with regards to how to handle missing data in the statistical analysis have been made in the statistical sections.

-Section 7.1.4, the following "[excluding palms, back of the hands, soles, scalp, genitals, and folds]" was removed as it was included in the protocol in error.

-Synopsis, secondary pharmacokinetic endpoint revised to be consistent with section 3.

-Section 5.2, criterion # 16, bullet numbering corrected to be consistent with the numbering in the synopsis.

-Section 5.2, criterion # 37 (in version 1.0), revised to be consistent with criterion in the synopsis.

-Section 9.10, section title was corrected.

-Minor typographical errors corrected throughout the document.

3.0 / 07 February 2019	

- To revise the inclusion criterion related to body mass index (BMI) in order to allow wider pool of subjects access to the trial.

	

- Synopsis and Section 5.1, inclusion criterion #7, BMI was revised to <math>\leq 38 \text{ kg/m}^2</math>.

## STATEMENT OF COMPLIANCE

The trial will be conducted in accordance with the protocol, International Council for Harmonisation (ICH) Good Clinical Practice (GCP), the Declaration of Helsinki, and applicable local regulations. The principal investigator will assure that no planned deviation from, or changes to the protocol will take place without prior agreement from the sponsor and documented approval from the institutional review board (IRB) / ethic committee (EC), except where necessary to eliminate an immediate hazard(s) to the trial subjects. All personnel involved in the conduct of this study have completed ICH GCP training.

The protocol, informed consent form(s), recruitment materials, and all subject materials will be submitted to the IRB/EC for review and approval. Approval of both the protocol and the consent form must be obtained before any subject is enrolled. Any amendment to the protocol will require review and approval by the IRB/EC before the changes are implemented to the study. All changes to the consent form will be IRB/EC approved.

## LIST OF ABBREVIATIONS

AD	atopic dermatitis
AE	adverse event
ALT	alanine aminotransferase
ANCOVA	analysis of covariance
anti-HBc	antibody to hepatitis B core antigen
AST	aspartate aminotransferase
β-hCG	β-human chorionic gonadotropin
BMI	body mass index
BSA	body surface area
BUN	blood urea nitrogen
CK	creatinine kinase
CMH	Cochran Mantel Hansel
CONSORT	Consolidated Standards of Reporting Trials
CRF	case report form
CRP	C-reactive protein
CPK	creatine phosphokinase
CRO	contract research organization
CV	coefficient of variation
DSMB	Data and Safety Monitoring Board
DLQI	Dermatology Life Quality Index
EASI	Eczema Area and Severity Index
EC	ethic committee
ECG	electrocardiogram
eCRF	electronic case report form
EDC	electronic data capture
ET	early termination
FDA	Food and Drug Administration
FSH	follicle-stimulating hormone
GCP	Good Clinical Practice
GERD	Gastroesophageal reflux disease
GGT	gamma-glutamyl-transferase
HBsAg	hepatitis B surface antigen
HBV	hepatitis B virus
HCT	hematocrit
HCV	hepatitis C virus
HDL	high-density lipoproteins
Hgb	hemoglobin
HIV	human immunodeficiency virus
IB	investigator brochure
ICH	International Council for Harmonisation
IGA	Investigator Global Assessment
IRB	institutional review board
ITT	intent-to-treat (population)

IWRS	Interactive Web Response System
LDH	lactate dehydrogenase
LDL	low-density lipoproteins
LMW	low molecular weight
JAK	janus kinase
Mapi	Mapi Life Sciences
MCH	mean corpuscular hemoglobin
MCHC	mean corpuscular hemoglobin concentration
MCV	mean corpuscular volume
MedDRA	Medical Dictionary for Regulatory Activities
MMRM	Mixed Model Repeated Measures
MPV	mean platelet volume
NRS	numeric rating scale
NSAID	nonsteroidal anti-inflammatory drug
NYHA	New York Heart Association
OLE	open label extension study
PD	pharmacodynamic
PK	pharmacokinetic
PLT	platelets
POEM	Patient-Oriented Eczema Measure
PP	per-protocol (population)
PPD	purified protein derivative
PUVA	psoralen-UV-A
QC	quality control
RBC	red blood cell (count)
RNA	ribonucleic acid
SAE	serious adverse event
SAF	safety (population)
SAP	statistical analysis plan
SCORAD	SCORing Atopic Dermatitis
SD	standard deviation
SYK	spleen tyrosine kinase
TB	tuberculosis
TEAE	treatment-emergent adverse event
ULN	upper limit of normal
UV	ultraviolet
VTE	venous thromboembolic event
WBC	white blood cell (count)
WHO	World Health Organization
WOCBP	women of childbearing potential

# 1 PROTOCOL SUMMARY

## 1.1 Synopsis

Name of Sponsor/Company: Asana BioSciences, LLC	Name of Investigational Product: ASN002	Name of Active Ingredient: ASN002
Title of Study: A Randomized, Double-Blind, Placebo-Controlled, Phase 2b Study to Evaluate the Efficacy, Safety, Tolerability, and Pharmacokinetics of ASN002 in Subjects with Moderate to Severe Atopic Dermatitis		
Phase of Development: Phase 2b		
Study Center(s): Approximately 50 study centers located in the United States, Canada, and Germany will participate in this study.		
Number of Subjects (planned): Approximately 220 subjects will be included in this study to reach 160 evaluable subjects.		
Duration of Study: The maximum study duration per subject is up to 20 weeks (including up to 4 weeks for the screening period, up to 12 weeks for the treatment period, and up to 4 weeks for the follow-up period).		
Investigational Product, Dosage, and Mode of Administration: ASN002 40, 60, or 80 mg or placebo orally administered once daily for 12 weeks. ASN002 will be available in 20-mg strength tablets.  Subjects will be randomized in a 1:1:1:1 ratio. Randomization will be stratified by baseline disease severity ([Eczema Area and Severity Index (EASI) = 16.0-21.2] vs. [EASI =21.3-29.9] vs. [EASI = $\geq$ 30.0]) and biopsy collection.		
Objectives: Primary: 

To evaluate the efficacy of ASN002 in subjects with moderate to severe atopic dermatitis (AD)

 Secondary: 

To evaluate the safety and tolerability of ASN002 in subjects with moderate to severe AD

To evaluate the pharmacokinetic (PK) profile of ASN002 in subjects with moderate to severe AD

 Exploratory: 

To assess population PK of ASN002 in AD subjects via a population PK analysis approach

To evaluate pharmacodynamic (PD) and biomarkers for evidence of drug activity in subjects with moderate to severe AD

		

Name of Sponsor/Company: Asana BioSciences, LLC	Name of Investigational Product: ASN002	Name of Active Ingredient: ASN002

• To explore the relationships between PK exposure and clinical measurement (e.g., biomarker, efficacy, and safety) as appropriate

		
Endpoints:		
Primary Endpoint:		


• Change from baseline in EASI score at Week 12

		
Secondary Endpoints:		
Secondary efficacy endpoints include:		

• Change from baseline in EASI score at Weeks 2, 4, and 8

• Percent change from baseline in EASI score at Weeks 2, 4, 8, and 12

• Proportion of subjects with at least a 50% reduction from baseline in EASI (EASI50) at Weeks 2, 4, 8, and 12

• Proportion of subjects achieving at least a 75% reduction from baseline in EASI (EASI75) at Weeks 2, 4, 8, and 12

• Proportion of subjects achieving at least a 90% reduction from baseline in EASI (EASI90) at Weeks 2, 4, 8, and 12

• Time to achieve EASI50, EASI75, and EASI90 relative to baseline.

• Proportion of subjects achieving at least a 2-grade reduction from baseline to clear (0) or almost clear (1) in Investigator's Global Assessment (IGA) at Weeks 2, 4, 8, and 12

• Proportion of subjects achieving at least a 2-grade reduction from baseline in IGA at Weeks 2, 4, 8, and 12

• Proportion of subjects achieving an IGA of clear (0) or almost clear (1) at Weeks 2, 4, 8, and 12

• Change from baseline in SCORing Atopic Dermatitis (SCORAD) at Weeks 2, 4, 8, and 12

• Change from baseline in 5-D Pruritus Scale at Weeks 2, 4, 8, and 12

• Change and percent change from baseline in single daily timepoint pruritus Numeric Rating Scale (NRS) at Week 1

• Change and percent change from baseline in weekly average of the peak daily pruritus NRS at Weeks 1, 2, 4, 8, and 12

• Proportion of subjects achieving at least a 4-point reduction from baseline in weekly average of the peak daily pruritus NRS at Weeks 1, 2, 4, 8, and 12

• Change and percent change from baseline in Body Surface Area (BSA) involved with AD at Weeks 2, 4, 8, and 12

• Change from baseline in Patient-Oriented Eczema Measure (POEM) at Weeks 2, 4, 8, and 12

• Change from baseline in Dermatology Life Quality Index (DLQI) at Weeks 2, 4, 8, and 12

		
Secondary safety endpoints include:		

• Number of treatment-emergent adverse events (TEAEs)

• Number of drug-related TEAEs

• Proportion of subjects withdrawing from worsening AD at Weeks 2, 4, 8, and 12

		

Name of Sponsor/Company: Asana BioSciences, LLC	Name of Investigational Product: ASN002	Name of Active Ingredient: ASN002


Changes in vital signs, physical examinations, electrocardiogram (ECG), and safety laboratory tests

		
Secondary pharmacokinetic endpoint includes: 

Measurement of plasma concentrations of ASN002 in all subjects receiving ASN002 treatment

		
Exploratory Endpoints:		
Exploratory endpoints include: 

Change from baseline in expression levels and kinase activity of key disease pathways in skin biopsies, such as Th2 and other T helper cell axes

Changes from baseline in cellular infiltrates of T-cells and dendritic cells

Changes from baseline in epidermal hyperplasia measures (epidermal thickness, ki67, and K16 expression)

Changes from baseline in mRNA and protein expression of differentiation markers

Changes in inflammatory measures in peripheral blood using proteomics

Characterization of population PK parameters via nonlinear mixed-effects modeling

Changes from baseline in clinical safety, efficacy, and biomarker measurements in relationship to PK exposure

		

Name of Sponsor/Company: Asana BioSciences, LLC	Name of Investigational Product: ASN002	Name of Active Ingredient: ASN002
---	--	---

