3.4 Randomization, Replacement, and Unblinding Procedures

Approximately 220 subjects will be randomized in a 1:1:1:1 ratio to receive either ASN002 40 mg, 60 mg, or 80 mg, or placebo, in order to complete the study with 160 evaluable subjects.

Randomization will occur prior to first dosing, at Day 1 visit. The randomization list will be generated using a validated software. Randomization will be stratified by baseline disease severity at Day 1 ([EASI = 16.0-21.2] vs. [EASI = 21.3-29.9] vs. [EASI = \geq 30.0]) and biopsy collection. The master randomization list will be kept secured until the study blind is broken at the end of study. This list will be uploaded into an Interactive Web Response System (IWRS). The investigator or designee will be able to acquire a randomization number for eligible subjects by connecting to the IWRS.

This study will be double-blinded. At all times, treatment and randomization information will be kept confidential and will not be released to the investigator, the study staff, the contract research organization (CRO), or the sponsor's study team until after the conclusion of the study.

Safety oversight will be under the direction of an independent DSMB, who will remain unblinded during the study.

	STATISTICAL ANALYSIS PLAN, Version Final 2.0
Protocol Number: ASN002AD-201 V3.0	Sponsor: Asana BioSciences, LLC

Blinding codes should only be broken in emergency situations for reasons of subject safety. If unblinding the treatment assignment for a subject is necessary due to a medical emergency (an unexpected SAE per product's safety profile) and other significant medical situations such as pregnancy, the investigator can make the decision to unblind the treatment assignment if knowing the treatment assignment will help treatment decision of the particular AE. When the blind for a subject has been broken, the reason must be fully documented in the source document and eCRF. Whenever possible, the investigator should contact the sponsor or its designee before breaking the blind. If the blind is broken, the investigator should promptly inform the medical monitor. Documentation of breaking the blind should be recorded with the date/time and reason why the blind was broken, and the names of the personnel involved.

The subject for whom the blind has been broken will be discontinued from the study and undergo the ET procedures.

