12 EFFICACY ANALYSIS

12.1 Primary Efficacy Endpoint

The EASI total score for four anatomic sites—head, upper extremities, trunk, and lower extremities—are assessed for erythema, induration/infiltration (papules), excoriation, and lichenification as seen on the day of the examination. The severity of each sign is assessed using a 4-point scale (half steps are allowed):

- 0 = none
- 1 = mild
- 2 = moderate
- 3 = severe

The area affected by atopic dermatitis within a given anatomic site is estimated as a percentage of the total area of that anatomic site and assigned a numerical value according to the degree of atopic dermatitis involvement as follows:

- 0 = no involvement
- 1 = <10%

	STATISTICAL ANALYSIS PLAN, Version Final 2.0
Protocol Number: ASN002AD-201 V3.0	Sponsor: Asana BioSciences, LLC

- 2 = 10% to <30%
- 3 = 30% to <50%
- 4 = 50% to <70%
- 5 = 70% to <90%
- 6 = 90% to 100%

The EASI score is obtained by using the formula below:

$$\text{EASI} = 0.1 (\text{Eh} + \text{Ih} + \text{Exh} + \text{Lh}) \text{Ah} + 0.2 (\text{Eu} + \text{Iu} + \text{Exu} + \text{Lu}) \text{Au} + 0.3 (\text{Et} + \text{It} + \text{Ext} + \text{Lt}) \text{At} + 0.4 (\text{El} + \text{Il} + \text{Exl} + \text{Ll}) \text{Al}$$

Where E, I, Ex, L, and A denote erythema, induration, excoriation, lichenification and area, respectively, and h, u, t, and l denote head, upper extremities, trunk, and lower extremities, respectively. The score will be set to missing in case of at least one missing value.

Descriptive statistics on EASI total score will be presented by visit for each treatment group. Change from baseline and percentage change from baseline will be also summarized.

Primary Endpoint Analysis

The primary efficacy endpoint is change from baseline in EASI score at Week 12. The primary efficacy analysis will be done using the mITT population and the PP population will be used as a supportive analysis.

A mixed effect model for repeated measures (MMRM) will be used to model the change from baseline in EASI score between treatments. The model will include treatment, visit, stratification factor (baseline disease severity, [EASI = 16.0-21.2] vs. [EASI = 21.3-29.9] vs. [EASI = \geq 30.0]), and treatment-by-visit interaction as fixed effects. The unstructured (UN) variance-covariance matrix and Kenward Roger degrees of freedom will be used.

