Information for stratification factor will be taken from the Electronic Data Capture (EDC) database, and not the IWRS for primary analysis.

Sensitivity Analyses

An analysis of variance (ANOVA) will be performed, where the absolute change from baseline in EASI score at Week 12 will be the dependent variable, the treatment group and stratification factor (baseline disease severity) will be fixed effects. A supportive analysis with pooled site and pooled

	STATISTICAL ANALYSIS PLAN, Version Final 2.0
Protocol Number: ASN002AD-201 V3.0	Sponsor: Asana BioSciences, LLC

site-by-treatment interaction included as fixed factors in addition to the other factors listed above will be performed in order to study the impact of pooled site on efficacy. If the pooled site-by-treatment interaction is not statistically significant, it will be removed from the model.

An additional sensitivity analysis will be carried out on the change from baseline in EASI score at Week 12 where data from site 029 is excluded.

Distribution of residuals will be visually examined to determine whether substantial departures from normality and homogeneity of variance are apparent. If the data are inconsistent with the assumption of normality, a nonparametric analysis of variance will be performed.

Additional sensitivity analyses will be performed using the stratification factor as per IWRS database in the primary efficacy MMRM model described above and including all efficacy EASI data for these subjects (before and after the prohibited medication).

	STATISTICAL ANALYSIS PLAN, Version Final 2.0
Protocol Number: ASN002AD-201 V3.0	Sponsor: Asana BioSciences, LLC

Subgroup Analyses

An analysis of variance (ANOVA) will be performed, where the absolute change from baseline or the percent change from baseline in EASI score at Week 12 will be the dependent variable, the treatment group and stratification factor as per EDC (baseline disease severity, [EASI = 16.0-21.2] vs. [EASI = 21.3-29.9] vs. [EASI = \geq 30.0] and treatment-by-stratification factor will be fixed effects. Treatment effect per stratification factor subgroup will be presented as well as associated p-values.

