1. If one question is left unanswered this is scored 0 and the scores are summed and expressed as usual out of a maximum of 30.
2. If two or more questions are left unanswered the questionnaire is not scored.
3. If question 7 is answered 'yes' this is scored 3 even if in the same question one of the other boxes is ticked.
4. If question 7 is answered 'no' or 'not relevant' but then either 'a lot' or 'a little' is ticked this is then scored 2 or 1. If it is answered 'no', but the second half is left incomplete, the score will remain 0.

DLQI will be assessed as

- the change from baseline in DLQI at Weeks 2, 4, 8, and 12.

Secondary Endpoint Analyses

The same methods (MMRM and ANOVA) as described for the primary efficacy analyses (Section 12.1) will be performed to analyze the change and percent change in EASI.

Similar methods (MMRM and ANCOVA) as described for the primary efficacy analyses (Section 12.1) will be performed to analyze the change and percent change in NRS, SCORAD (MMRM and ANCOVA for total score; MMRM only for sleep and pruritus sub-scores) and BSA, and the change in 5D-Pruritus Scale (change from baseline only), POEM (change from baseline only) and DLQI (change from baseline only), with the addition of the baseline score as covariate in the models. Analyses will be based on the mITT population for all secondary parameters.

For categorical efficacy endpoints involving proportions of IGA, EASI and NRS (e.g. the proportion of subjects achieving at least a 2-grade reduction from baseline to clear (0) or almost clear (1) in Investigator's Global Assessment (IGA) at week 12), a Cochran Mantel Hansel test (CMH) controlling for the stratification variable (baseline disease severity) will be performed. For subgroup analyses at each level of baseline severity, a Chi-squared test will be performed. Analyses will be based on the mITT population for all secondary parameters and also on PP population for IGA.

	STATISTICAL ANALYSIS PLAN, Version Final 2.0
Protocol Number: ASN002AD-201 V3.0	Sponsor: Asana BioSciences, LLC

As a sensitivity analysis for IGA, the Cochran Mantel Hansel test (CMH) controlling for the stratification variable (baseline disease severity) will be performed, excluding the subjects for whom the IGA form was initially used to capture the vIGA assessment at baseline. This sensitivity analysis will be performed on the mITT and PP populations.

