Additional exploratory analyses may be performed to further understand the impact, if the results of the sensitivity analyses excluding the subjects for whom the IGA form was initially used to capture the vIGA assessment at baseline reveal inconsistencies with the results including those subjects.

The time to achieve the 50%, 75%, or 90% reduction in EASI relative to baseline and the time to achieve a 4-point reduction from baseline in weekly average of the peak daily pruritus NRS will be compared between treatments using the Kaplan Meier method. A subject will be considered as censored if he has not met the event of interest at the end of the study (Week 12 visit) or if the subject is lost to follow up at last observation. Those subjects will be censored at their last available EASI (or NRS) assessment.

Information for stratification factors will be taken from the EDC database, and not the IWRS for all secondary endpoint analyses.

Descriptive statistics will be presented on all secondary endpoints by visit and treatment group.

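### SAP 12.2 names no test, effect measure or strata for time to EASI50/75/90 and time to the 4-point NRS response; a log-rank test and Cox model stratified by baseline severity would close the gap at almost no cost

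*Protocol*

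**What the plan says.** - **Endpoint.** Protocol 1.1 and 3 list "Time to achieve EASI50, EASI75, and EASI90 relative to baseline" among the secondary efficacy endpoints and attach no method. The time to a 4-point NRS reduction appears only in the SAP (2 and 12.2).
- **Comparison.** SAP 12.2 says that both kinds of time "will be compared between treatments using the Kaplan Meier method". A subject is "censored if he has not met the event of interest at the end of the study (Week 12 visit"), or if lost to follow-up; the censoring time is the last available assessment. Nothing more is said about the comparison.
- **Randomisation.** SAP 3.4: "Randomization will be stratified by baseline disease severity at Day 1", in the bands EASI 16.0-21.2, 21.3-29.9 and 30.0 or more. Biopsy collection is the second factor.
- **Other efficacy analyses.** For the primary MMRM (SAP 12.1), "The model will include treatment, visit, stratification factor (baseline disease severity" among other terms. For the ANOVA, "the treatment group and stratification factor (baseline disease severity) will be fixed effects". SAP 12.2 uses similar models, with baseline score added, for the other continuous endpoints. The responder endpoints, including EASI50/75/90, get a CMH test "controlling for the stratification variable (baseline disease severity) will be performed".
- **Exceptions.** SAP 3.5 drops the biopsy factor from all models as purely operational. It gives no reason for leaving severity out of the time-to-response comparison.
- **Data source.** SAP 12.2 takes stratification data for the secondary analyses from EDC rather than IWRS.
- **Error rate.** Tests are two-sided at 0.05 (SAP 5.6). Secondary p-values are nominal, with no multiplicity adjustment (SAP 6.5).

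**The concern.** A Kaplan-Meier analysis gives one curve per arm. It does not by itself compare arms, so the programmer has to choose a test. The default choice is a log-rank test without strata.

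After randomisation balanced within severity bands, that default has a known weakness. Its variance estimate takes no credit for the balance, so if severity predicts response the true size falls below 5%. Pooling bands with different response rates also pulls the marginal contrast between arms towards the null. Both effects cost power.

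At stake are the speed-of-response results, which are listed secondary endpoints. They would be the only between-arm efficacy comparison in the plan specified without the severity factor. The choice of test would also be left to the analyst.

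**Working it through.** **1. The plan's own figures.** None of the sample-size figures concerns a time-to-event endpoint, but they reproduce.
- Primary (SAP 5.1): difference 15 - 8 = 7, SD 8, n = 40 per group, alpha 0.0167. The noncentrality is 7 / (8 x sqrt(2/40)) = 3.91 with 78 degrees of freedom, giving power 92.6% (stated: 92%).
- IGA: 37.5% vs 11.1%, 46 per group, Fisher exact test at 0.05: power 80.0% (stated: 80%).
- Dropout: 46 / 0.85 = 54.1, so 55 per group (stated: 55).

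No event rate, hazard ratio or power is given for time to response.

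**2. Simulation inputs.**
- From the documents: 55 per arm, about 15% dropout, EASI at Weeks 2, 4, 8 and 12, three severity bands, two-sided 0.05, and the IGA rates 11.1% and 37.5%.
- Assumed: a log-rank test; near-equal bands (36, 36 and 38 subjects over the two arms compared) balanced between arms; exponential times; the other Week 12 response rates; and SR, the hazard ratio between adjacent bands, from 1 to 3 (band multipliers SR, 1 and 1/SR).

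**3. Treatment effect.** HR = ln(1 - p1) / ln(1 - p0), where p0 and p1 are the Week 12 response rates on placebo and active:
- 40% vs 65%: ln 0.35 / ln 0.60 = 2.06
- 20% vs 45%: ln 0.55 / ln 0.80 = 2.68
- 11.1% vs 37.5%: ln 0.625 / ln 0.889 = 3.99

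The HR within bands and the overall placebo rate are held fixed as SR changes. The overall active rate therefore drifts down. In the first scenario it is 65% at SR 1, 62.1% at SR 2 and 58.7% at SR 3. The fair comparison is within a row.

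**4. Test.** Z = sum(O - E) / sqrt(sum V) over visits. The stratified version forms O - E and V within each band and then adds them. There were 40,000 runs per cell, so the Monte Carlo standard error near 73% power is sqrt(0.73 x 0.27 / 40,000) = 0.2 points.

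**5. Results, unstratified then stratified.**

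| Rates (assumed unless noted) | SR | Power | Gain (points) | Type I error |
|---|---|---|---|---|
| 40% vs 65% | 1.0 | 73.4% / 73.0% | -0.4 | 5.2% / 5.2% |
| | 1.25 | 72.4% / 72.9% | 0.5 | 4.9% / 5.1% |
| | 1.5 | 70.5% / 72.5% | 2.0 | 4.8% / 5.2% |
| | 2 | 64.9% / 71.7% | 6.8 | 4.0% / 5.2% |
| | 3 | 51.8% / 70.1% | 18.3 | 2.5% / 5.0% |
| 20% vs 45% | 1.0 | 77.7% / 77.4% | -0.3 | 5.0% / 5.0% |
| | 1.5 | 76.1% / 77.2% | 1.1 | 4.7% / 4.9% |
| | 2 | 73.6% / 76.8% | 3.2 | 4.5% / 5.1% |
| | 3 | 66.8% / 75.5% | 8.7 | 3.7% / 5.0% |
| 11.1% vs 37.5% (IGA rates, SAP 5.1) | 1.0 | 89.2% / 89.1% | -0.1 | 4.9% / 4.8% |
| | 1.5 | 88.3% / 88.9% | 0.6 | 4.8% / 4.9% |
| | 2 | 86.6% / 88.2% | 1.6 | 4.7% / 5.0% |
| | 3 | 83.6% / 87.4% | 3.8 | 4.3% / 4.9% |

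**6. What the SR values mean.** In the 40% scenario, solving for the baseline hazard gives placebo response by band of 52.8%, 39.4% and 28.4% at SR 1.5; 61.7%, 38.1% and 21.3% at SR 2; and 72.8%, 35.2% and 13.5% at SR 3. The last is a very wide spread.

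**7. Cross-check with other inputs.** A separate simulation (3,000 runs) used visit hazards of 0.08, 0.10, 0.12 and 0.12 in the middle band, multipliers 2 : 1 : 0.4 and HR 2.0. Power was 56.8% unstratified and 65.2% stratified, and size 3.6% and 5.0%. With equal multipliers both tests had 66.3% power. The pattern is the same.

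**The case against.** The strongest reply is that SAP 12.2 does not prescribe an unstratified test. It names no test, and an unnamed test has no size or power to criticise. That stands: a reader might infer that the plan has chosen a conservative analysis, but the text is silent. The EDC sentence does not fill the silence, because it says where stratum data come from and not which analyses use them.

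The second reply is that the loss may be trivial. EASI50/75/90 are percentage reductions from the subject's own baseline, so they are already scaled for severity. No passage shows that the baseline band predicts relative response. This also stands. It is why the size can be given only as a range whose lower end is zero.

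Three further inferences are tempting and not supported:
- *The same loss applies to the NRS endpoint.* The stratum is EASI severity and not itch, and NRS averages are analysed at Weeks 1, 2, 4, 8 and 12. The simulation does not model that endpoint.
- *The Week 12 EASI75 CMH test and the time-to-EASI75 comparison could disagree only because one is stratified.* They measure different things: status at one visit, against first attainment with censoring. They can differ under identical stratification.
- *The set of comparisons is too conservative.* Conservatism would apply to each single test. Three doses at an unadjusted 0.05 give 1 - 0.95^3 = 14.3% family-wise error per endpoint if independent, and somewhat less with a shared placebo arm.

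None of these replies gives a reason to leave the comparison undefined, or to omit a factor that the rest of the efficacy plan uses.

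**Conclusion.** The point holds in conditional form. The time-to-response comparison lacks a test, an effect measure and strata, although severity is a randomisation factor and is carried through the other between-arm efficacy analyses.

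If the default unstratified log-rank test is used and severity is prognostic, each test is somewhat conservative and loses power. Across the three scenarios the loss is about 0 to 2 points up to SR 1.5, 1.6 to 7 at SR 2, and 4 to 18 at SR 3. It rests on the assumed response rates, exponential times, near-equal bands and the log-rank choice. The documents give no prognostic strength, so no single figure in that range can be called the expected one.

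Stratifying when severity does not matter costs at most 0.4 points here (73.4% to 73.0%), which makes the change a nearly free improvement. The primary analysis is not affected, and no multiplicity-controlled claim rests on these endpoints.

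**What to change.** Amend the time-to-response paragraph of SAP 12.2; the Protocol endpoint lists need no change.
- Keep the Kaplan-Meier curves by arm for display.
- Compare each dose with placebo by a two-sided log-rank test stratified by the three baseline severity bands as recorded in EDC.
- Report a hazard ratio with 95% CI from a Cox model stratified by the same factor.
- State how ties are handled, since EASI is scheduled only at Weeks 2, 4, 8 and 12 and many event times will coincide.
- Say that the p-values are nominal, in line with SAP 6.5.

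The cost is a sentence or two in the SAP and a strata option in the program, with no new data. Made before unblinding, the change also takes the choice of test out of the analyst's hands.
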